3. GENERAL STATISTICAL CONSIDERATIONS

3.1. Descriptive statistics

Descriptive statistics will be provided by treatment group, and all treatment groups pooled (for analyses on disposition of patients, baseline characteristics and patient follow-up, and on adverse events).

For **qualitative data**, number of observed values, number and percentage of patients per class will be presented. Unless otherwise specified in the TLG, no class "Missing" is considered.

For **quantitative data**, number of observed values, mean, standard deviation, median, first and third quartiles, minimum and maximum will be presented.

For **event data**, number of patients having experienced the event (n) and number of events that occurred (for AE analyses only) (NAE) will be presented.

3.2. General definitions

Patients having taken at least one dose of IMP correspond to patients with at least one date of first and/or last IMP intake complete or partially complete.

Analysable value will be defined as any non-missing value, except for:

- Laboratory parameters:
 - A laboratory value is considered as analysable if non-missing and not flagged in the ClinTrial database as "not analysable".
 - Vital signs value is considered as analysable if collected under appropriate circumstances (corresponds to the item of the source database).

Baseline value will be defined as the last analysable value prior to the first IMP intake. In case of patient included and/or randomised but not having taken at least one dosage of IMP: value at baseline is defined as the last analysable value prior or equal to date of inclusion visit.

Considered periods are:

- ASSE-W013 period.
- ASSE-W028 period.

Last post-baseline value under treatment of the period will be defined as the last post-baseline analysable value under treatment during the considered period.

Change from baseline to post-baseline visit is calculated as: Value at the post-baseline visit - Value at baseline.

Change from baseline to post-baseline visit under treatment is calculated as: Value at the post-baseline visit under treatment - Value at baseline.

Change from baseline to last post-baseline value under treatment is calculated as: Last post-baseline value under treatment - Value at baseline.

For safety endpoints (except adverse events), the following definition will be applied:

- **High emergent abnormal value under treatment according to the laboratory reference ranges** is defined as value \leq ULN (Upper Limit of Normal laboratory reference range) or missing at the baseline of the treatment period and $>$ ULN under treatment.
- **Low emergent abnormal value under treatment according to the laboratory reference ranges** is defined as value \geq LLN (Lower Limit of Normal laboratory reference range) or missing at baseline of the treatment period and $<$ LLN under treatment.

- **High emergent abnormal value under treatment according to the cut-offs for PCSA** values is defined as value \leq ULS (Upper Limit used to define potentially clinically Significant abnormal values) or missing at baseline of the treatment period and $>$ ULS under treatment.
- **Low emergent abnormal value under treatment according to the cut-offs for PCSA** values is defined as value \geq LLS (Lower Limit used to define potentially clinically Significant abnormal values) or missing at baseline of the treatment period and $<$ LLS under treatment.

Other calculation rules for general definitions (such as value prior to treatment / under treatment, first and last IMP intake dates...), are provided in [Appendix 7.1](#).

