5. INCLUSION AND WITHDRAWAL OF PATIENTS

5.1. Inclusion criteria

All patients included should present the following characteristics:

1. Male or female aged between 18 to 75 years (both inclusive),
2. Patients must have a body mass index (BMI) of 18 (exclusive)-40 (inclusive),
3. Diagnosis of primary Sjögren's Syndrome based on 2016 ACR-EULAR criteria ([Appendix 2](#)),
4. ESSDAI total score ≥ 6 during screening, with at least 6 points scored within the 7 following domains: constitutional, lymphadenopathy, glandular, articular, cutaneous, hematologic and biologic,
5. Positive anti-SSA (Ro) antibodies or anti-nuclear antibodies (ANA) $\geq 1:320$ or rheumatoid factor (RF) > 20 IU/ml during screening period, measured in a central laboratory,
6. Stimulated whole salivary flow rate > 0 mL/minute,
7. Negative Tuberculosis test (Quantiferon or T-Spot test) during screening,
8. A chest x-ray obtained during the screening period or anytime within 90 days prior to signing the ICF with no evidence of current active infection (e.g. TB), malignancy, or clinically significant abnormalities (unless due to pSS),
9. All vaccinations deemed necessary by the investigator for the patient, up to date,
10. Female patient is postmenopausal, surgically sterile (having had a hysterectomy or bilateral oophorectomy) and/or is using a highly effective method of contraception (described in [Section 5.3](#)) until the last follow-up visit. In case of use of oral contraception women should have been stable on the same contraceptive drug for at least 3 months prior to the first IMP administration,
11. Non-vasectomized male patients having a female partner of childbearing potential must agree to the use of a highly effective method of contraception from first IMP administration until the last follow-up visit,
12. Willing to adhere to the prohibitions and restrictions specified in this protocol,
13. Signed written informed consent (obtained as described in [Section 13.3](#) of the protocol).

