4.4.1. Adverse events

Definition:

- **Treatment Emergent Adverse Events (TEAE)** on the ASSE-W013 period are defined as all adverse events:

- Which occur between the infusion start date/time of the first IMP intake (included) and the date of W013 visit (included) or the last IMP intake date + 21 days (included) if the W013 visit has not been done

or

- Which occur before the infusion start date/time of the first IMP intake and which worsen (in terms of intensity) or become serious according to the investigator opinion between the infusion start date/time of the first IMP intake (included) and the date of W013 visit (included) or the last IMP intake date + 21 days (included) if the W013 visit has not been done.

Of note, in case of multiple information of the same event before the first IMP intake date, the information nearest to the first IMP intake date is taken into account.

- **Treatment Emergent Adverse Events (TEAE)** on the ASSE-W028 period are defined as all adverse events:

- Which occur between the infusion start date/time of the first IMP intake (included) and the last IMP intake date + 85 days (included),

or

- Which occur before the infusion start date/time of the first IMP intake and which worsen (in terms of intensity) or become serious according to the investigator opinion between the infusion start date/time of the first IMP intake date (included) and the last IMP intake date + 85 days (included).

Of note, in case of multiple information of the same event before the first IMP intake date, the information nearest to the first IMP intake date is taken into account.

Analysis:

Number of events, number and percentage of patients reporting at least one event, presented by primary system organ class, and/or preferred term (depending on the analysis), will be provided for:

- Serious adverse events (SAE) over the analysed period according to the investigator or sponsor opinion.
- Adverse events of special interest.
- Treatment Emergent Adverse Event (TEAE).
- TEAE leading to IMP withdrawal.
- TEAE requiring new treatment or increase of on-going treatment.
- TEAE requiring surgical or medical procedure.
- TEAE related to IMP.
- TEAE related to Pss.
- Serious TEAE.
- Serious TEAE related to IMP.
- TEAE of Grade 3-4 intensity.
- Non serious TEAE over the corresponding treatment period.

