4.4.2. Clinical laboratory evaluation

4.4.2.1. Blood samplings for haematology, biochemistry and coagulation

For each laboratory parameter, the following analyses will be performed:

- Descriptive statistics on value at baseline, on value at each post-baseline visit under treatment, on last post-baseline value under treatment and on change from baseline to last post-baseline value under treatment. These analyses will be performed on both periods (ASSE-W013 and ASSE-W028) only for haematology parameters and on ASSE-W028 for other parameters.
- Number and percentage of patients with at least one high/low emergent abnormal value under treatment, according to the laboratory reference ranges and to the cut-offs for PCSA values.
- Laboratory parameters classified (number and percentage of patients in each class) according to these reference ranges and cut-offs and using shift tables from baseline to the worst (high and/or low) values under treatment.

Moreover, listings of patients with out-of-range or PCSA analysable values emergent under treatment and of non-analysable values excluded from analyses will be provided.

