- Only ULN and ULS will be considered as clinically relevant for Alanine Aminotransferase, Alkaline phosphatase, Amylase, Aspartate Aminotransferase, Basophils, Basophils/Leucocytes, Bilirubin, C reactive Protein, Cholesterol, Creatine Kinase, Direct Bilirubin, Eosinophils, Eosinophils/Leukocytes, Gamma Glutamyl Transferase, Indirect Bilirubin, Lactate dehydrogenase, Triglycerides.
- Only LLN, ULN and ULS will be considered as clinically relevant for Creatinine, Monocytes, Monocytes/Leukocytes, Protein, Triacylglycerol Lipase, Uric acid.
- Only LLN and ULN will be considered as clinically relevant for Activated partial thromboplastin time, Albumin (%) in total protein, Erythrocyte Sedimentation Rate, Prothrombin time, Urea.
- Only ULN will be considered as clinically relevant for Rheumatoid Factor.
- All limits (LLS, LLN, ULN and ULS) will be considered as clinically relevant for other parameters.
- Note: For Glucose parameter, whatever the condition (fasting or not), the laboratory reference ranges and PCSA values of Glucose in fasting condition will be considered.
- For parameters with mandatory limits of normal laboratory reference ranges, in the situation where these limits are outside the limits used to define PCSA values, the normal laboratory reference limits will be substituted by the corresponding PCSA limits
- Each non missing value will be classified taking into account clinically relevant (reference/PCS) limit (*i.e.* the value will only be compared to the clinically relevant limit(s) and will be considered as normal if not out of this (those) limit(s)).

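### SAP 3.2 has no category for blood counts that worsen from an already low baseline, so some falls on treatment reach no emergent laboratory count or listing

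*SAP*

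**What the plan says.** SAP 3.2 defines a low emergent value on two tiers. On the reference-range tier the value must have been at or above "LLN (Lower Limit of Normal laboratory reference range) or missing at baseline of the treatment period and" then below LLN under treatment. On the PCSA tier it must have been at or above "LLS (Lower Limit used to define potentially clinically Significant abnormal values) or missing at baseline of the treatment period and" then below LLS. Neither tier covers a value that was already low and became lower.

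SAP 4.4.2.1 builds three displays on these limits:

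- a count: "Number and percentage of patients with at least one high/low emergent abnormal value under treatment, according to the laboratory reference ranges", and likewise by PCSA cut-off;
- class tables, "using shift tables from baseline to the worst (high and/or low) values under treatment";
- "listings of patients with out-of-range or PCSA analysable values emergent under treatment".

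SAP 7.2.3.2 names the parameters for which only some limits matter. Lymphocytes, neutrophils, platelets and haemoglobin are not among them, so the default applies: "All limits (LLS, LLN, ULN and ULS) will be considered as clinically relevant for other parameters". The same section resets LLN to LLS where LLN would fall below it, so LLS never exceeds LLN.

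Protocol 5.1 requires an ESSDAI of at least 6, "with at least 6 points scored within the 7 following domains: constitutional, lymphadenopathy, glandular, articular, cutaneous, hematologic and biologic". Appendix 3 scores lymphocytes between 500 and 1000/mm3 as haematological activity. Exclusion criterion 29 removes only patients with, at screening, white cells below 1,500, neutrophils below 800, lymphocytes below 500 or platelets below 50,000 (all x10^6/L), or haemoglobin below 8 g/dL.

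**The concern.** An emergence rule that requires a normal baseline suits a population with normal counts. Here cytopenia is permitted at entry and can contribute to eligibility, and Protocol section 2 names lymphopenia as a risk that follows from the mechanism of action. Patients who start low have the least reserve, so the laboratory tables should be able to show whether they get worse on treatment.

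The SAP does recognise worsening of pre-existing conditions for adverse events. SAP 4.4.1 includes events "Which occur before the infusion start date/time of the first IMP intake and which worsen (in terms of intensity" or become serious. The laboratory rules have no counterpart. At stake is the completeness of a descriptive safety display: some objective falls would be neither counted nor listed by arm.

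**Working it through.** The documents state no figure on this point, so there is none to reproduce. The check applies the SAP 3.2 rules to every combination of baseline and worst value.

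| Baseline | Worst value on treatment | Reference-range emergent | PCSA emergent | Shift table |
|---|---|---|---|---|
| at or above LLN | below LLN | yes | yes, if below LLS | class changes |
| LLS to below LLN | below LLS | no | yes | class changes |
| LLS to below LLN | lower, but still at or above LLS | no | no | same class |
| below LLS | lower still | no | no | same class |

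The last two rows are the gap.

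**Lymphocyte examples** (x10^6/L; LLN of 1000 is an assumption, as are the LLS values):

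- 900 to 550 with LLS 500: neither tier.
- 900 to 450 with LLS 500 or 800: PCSA emergent, counted and listed.
- 700 to 450 with LLS 800: neither tier, but below 500 and therefore an adverse event of special interest under Protocol 8.6.

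**Sensitivity to LLS.** Take every lymphocyte baseline from the eligibility floor of 500 to 990, in steps of 10, and every lower value down to 0. That gives 50 + 51 + ... + 99 = 3,725 possible falls. The reference-range tier counts none of them. The PCSA tier counts (baselines at or above LLS) × (values below LLS). The last column also removes falls that end below 500, since those are of special interest.

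| Assumed LLS | PCSA emergent | On neither tier | On neither tier and not below 500 |
|---|---|---|---|
| 500 | 50 × 50 = 2,500 (67%) | 1,225 (33%) | 1,225 (33%) |
| 600 | 40 × 60 = 2,400 (64%) | 1,325 (36%) | 1,325 − 10 × 50 = 825 (22%) |
| 800 | 20 × 80 = 1,600 (43%) | 2,125 (57%) | 2,125 − 30 × 50 = 625 (17%) |
| 1000 (= LLN) | 0 | 3,725 (100%) | 3,725 − 50 × 50 = 1,225 (33%) |

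The same enumeration for the other counts gives these shares on neither tier:

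- Neutrophils (floor 800, assumed LLN 1800): 38% with LLS 800 or 1000, 65% with LLS 1500.
- Platelets (floor 50,000, assumed LLN 150,000): 50%, 43% and 50% with LLS 50,000, 75,000 and 100,000.
- Haemoglobin (floor 8 g/dL, assumed LLN 12): 20%, 40% and 72% with LLS 8, 9.5 and 11.
- All three: 100% if LLS equals LLN.

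The grid weights every fall equally, so these are not probabilities. They show that some falls go uncounted at every cut-off tried.

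**Other displays.** SAP 4.4.2.1 summarises change from baseline only to the last on-treatment value, not to the lowest. For the longer period SAP 7.1.1 extends that window to 85 days after the last infusion, so a count that fell and recovered can drop out of the change summary. Visit minima do not show the same patient's baseline.

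**The case against.** The strongest reply is that the plan has several other routes to these patients.

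- **PCSA tier and shift tables.** A low patient who crosses LLS is counted and listed, and moves off the shift-table diagonal. This stands.
- **Special-interest events.** Protocol 8.6 makes lymphopenia below 500x10^6/L an event of special interest with no baseline condition, Protocol 8.7 requires notification within 24 hours, Protocol 12.4 puts such events before the DSMB, and SAP 4.4.1 tabulates them. This stands for lymphocytes below 500 only; neutrophils, platelets and haemoglobin have no equivalent.
- **Adverse events.** Protocol 8.3 treats any worsening of an existing condition as an adverse event, so the two definitions can be read as complementary. This stands in part. Protocol 8.2 makes a laboratory value an adverse event only if it causes symptoms, is judged clinically significant or needs therapy. Protocol 8.8 grades it on clinical intensity, which may differ from the laboratory grade.

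Three stronger readings are tempting, and the documents do not support them. A reader might infer that patients enrolled with low counts can appear in no emergent count or listing at all; the first two routes show otherwise. A reader might infer that these patients are left in the percentage base while being removed from the numerator; SAP 4.4.2.1 states no denominator, and SAP 1 places the table templates in a separate document. A reader might infer that the trial selects for cytopenia; the haematological domain is one of seven that may supply the entry points, and none of the seven is individually required.

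**Conclusion.** The point holds in a limited form. A fall from a baseline already below LLS, or one that stays between LLS and LLN, enters no emergent laboratory count or listing and stays in the same shift-table class. For neutrophils, platelets and haemoglobin, and for lymphocytes that remain at or above 500x10^6/L, the only other route is an adverse event that depends on investigator judgement.

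The size cannot be given. It depends on LLN, LLS and the number of patients enrolled with low counts, and the documents give none of these. If LLS equals the eligibility floor, only a patient whose count dropped between screening and W000 could start below it, and the gap is then mainly the band between LLS and LLN. One uncounted patient is 1/30 = 3.3 percentage points if the base is the planned S95011 arm. This affects descriptive safety tables in a small phase IIa trial with DSMB review. It does not touch the primary analysis. It is a cheap improvement, not a defect that undermines the safety evaluation.

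**What to change.** Keep the emergent definitions in SAP 3.2 as they are. For lymphocytes, neutrophils, platelets and haemoglobin, add a separate category, worsened under treatment from an abnormal baseline, defined as an increase in laboratory CTCAE v5.0 grade from baseline to the worst on-treatment value. Report it by arm beside the emergent counts, and include these patients in the SAP 4.4.2.1 listing.

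Derive the grade from the laboratory value, not from the investigator's adverse event grade, because Protocol 8.8 lets the two differ. CTCAE v5.0 is already the protocol's safety scale. The Appendix 3 haematological bands are less suitable: they belong to an efficacy index, they exclude drug-induced cytopenia, and for lymphocytes the only threshold they add below the 500–1000 entry band is 500, which the special-interest definition already uses.

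The cost is one extra table row and listing, and slightly less favourable laboratory safety percentages. No new data are needed, since Protocol 8.2 has haematology drawn at every scheduled dosing and follow-up visit, and no eligibility, dosing or stopping rule changes. A fall within one CTCAE grade would still not be counted.

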4. STATISTICAL ANALYSES

Specific definitions and calculation rules are provided in [Appendix 7.2](#)

4.1. Study participant

4.1.1. Disposition

The size of each analysis set, and reasons for exclusion will be described.

Disposition of patients, including reasons for withdrawal, will be summarized during the study, overall and by visit, in the RS.

4.1.2. Protocol deviations

Protocol deviations before or at inclusion, as well as after inclusion, will be described in the RS for each considered period.

For the description of important protocol deviations, the 6 following categories are considered in accordance with [ICH E3](#) guideline and [ICH E3 Q&A](#):

- Selection/inclusion criteria not fulfilled.
- Patient having withdrawal criteria but not withdrawn.
- Incorrect treatment or dose received.
- Forbidden concomitant treatment.
- Endpoint assessment possibly affected.
- Safety possibly affected.

4.1.3. Demographic data and baseline characteristics

Demographic characteristics and other baseline characteristics will be summarized as follows, by treatment group and overall, in the RS:

- Demographic characteristics:
 - Age (years).
 - Sex: male / female.
 - Race: White / American Indian or Alaska Native / Asian / Black or African American / Native Hawaiian or other Pacific Islander / Other.
 - Ethnicity: Hispanic or Latino / not Hispanic or Latino.
 - Life habits:
 - Smoking (excluding e-cigarette): Never / Has stopped smoking / Current smoker.
 - E-cigarette: Yes / No.
 - Alcohol: No / Has stopped drinking / Currently drinking.
 - Caffeine: Yes / No.
- Baseline characteristics:
 - History of the primary Sjögren's syndrome:
 - Disease duration (years) and by class: ≤ 7 years / > 7 years.
 - Specific treatment for pSS for which a stratification was done at baseline Nothing / Oral corticosteroid / Antimalarial / Oral corticosteroid and antimalarial.
 - Relevant medical and surgical history other than the PSS symptoms (by SOC and PT).
 - Specific previous treatment (by ATC code and preferred name).
 - Non-specific previous treatment (by ATC code and preferred name).
 - ESSDAI total score overall and in severity classes: Mild < 5 / Moderate [5 – 14[/ Severe ≥ 14 .

- ESSDAI by domain: Constitutional / Lymphadenopathy and lymphoma / Glandular / Articular / Cutaneous / Pulmonary / Renal / Muscular / PNS / CNS / Haematological / Biological.
- ESSPRI total score overall and in classes: $< 5 / \geq 5$.
- ESSPRI by symptom: Dryness / Fatigue / Pain.
- SF-36 physical and mental scores.
- MFI by domain: General fatigue / Physical fatigue / Reduced activity / Reduced motivation / Mental fatigue.
- NRS: PhGA score and PGA total score.
- Schirmer test for the most affected eye and mean of both eyes.
- OSS for the most affected eye and mean of both eyes.
- Sialometry (stimulated and unstimulated salivary flow score).
- Weight (kg).
- Body temperature (°C).
- BMI (kg/m²) and by class: < 18.5 , $[18.5-25[$, $[25-30[$, ≥ 30 .
- SBP (mmHg).
- DBP (mmHg).
- HR (b.p.m).

4.2. Treatments of patients

4.2.1. Extent of exposure and treatment compliance

Number and percentage of patients by total number of infusions and time between two IMP administrations by visit will be described by treatment group in the RS and SS (if different).

4.2.2. Concomitant treatments

All specific (resp. non-specific) concomitant treatments taken at inclusion, during the W000-W013 period, and after the last IMP intake will be described in the RS and the SS (if different), by ATC code and preferred name and by treatment group.

4.3. Efficacy analyses

Calculation rules for efficacy endpoints and other specific definitions are provided in [Appendix 7.2.2](#).

4.3.1. Primary efficacy estimand

The primary estimand of interest is the effect of the treatments on the clinical disease activity in all patients assuming non-occurrence of intercurrent events (IE). The motivation for this choice is to assess at this proof-of-concept stage the full efficacy potential, that is, the pharmacologic effect of the S95011 if all patients adhere to it (without any intercurrent events).

The attributes of the primary estimand are defined as follow:

- **Treatment:** S95011 or placebo.
- **Population:** RS.
- **Variable:** change in ESSDAI total score from baseline to W013 (primary efficacy endpoint).
- **Summary measure:** difference in means between treatments.
- **Intercurrent events (IE):**
 - IE1: Study drug discontinuation for major worsening of primary Sjögren's syndrome.
 - IE2: Increase or initiation of authorized medication for pSS.
 - IE3: Study drug discontinuation for AE related to study drug.

- IE4: Study drug discontinuation for other reasons (non-medical reason, AE not related...).
- IE5: Switch of treatment group (error of dispensation).
- IE6: Decrease or stop of authorized medication for pSS.

The rate of IEs is assumed to be below 10%. They will be handled by a hypothetical strategy to estimate what the outcome would have been at the designated time point if no IE would have occurred through that time point, considering that patients with IE would have efficacy outcomes as patients, in their treatment group, who continue their treatment without IE.

Note: In case a patient is concerned by several IEs, the first event will be considered. If several IE occurred the same day, IE will be considered to be more conservative in the following order: IE1; IE2; IE3; IE4; IE5, IE6.

